2.1 Metabolic Syndrome

The term "metabolic syndrome" (MetS) first appeared in German-speaking countries in 1980 and is also known as the "deadly quartet". It describes a combination of elevated blood sugar levels, high blood pressure, a disturbed fat and cholesterol balance and obesity with abdominal fat distribution (Pott, 2007).

Metabolic syndrome (MetS) is an important driver of the current global cardiovascular crisis. It significantly increases the risk of type 2 diabetes, cardiovascular disease (CVD), and premature death. Genetic polymorphisms, inflammation, endocrinopathies, and unhealthy lifestyle contribute to the association between metabolic syndrome and a number of psychiatric disorders (Ho et al., 2014).

MetS is a combination of clinical signs and laboratory findings that includes five key features: obesity, elevated blood pressure, reduced levels of serum high-density cholesterol (HDL-c), increased levels of serum triglycerides, and high serum levels of fasting glucose. (Noubiap et al., 2022). Metabolic syndrome is generally diagnosed when a patient presents with at least three of its defining components (Grundy, 2008; NCEP, 2001).

Metabolic syndrome is a major public health problem that has been recognized to be a global epidemic by the World Health Organization (WHO) (Saklayen, 2018).

According to the Austrian Social Insurance, 30 to 40 percent of the population have a high health risk of civilization diseases such as MetS or COPD (Hartl, 2020). Around 25% of the Austrian population is affected by MetS, which is caused by sedentary life-styles, stress, smoking, alcohol consumption, a diet high in fat and cholesterol, increased salt intake, and obesity (Codazzi et al., 2023; Hartl, 2020).

2.1.1 Definition of MetS for the inclusion in the study NATURE-MET-S

The NATURE-MET-S study will use the ATP III criteria (Adult Treatment Panel III of the National Cholesterol Education Program) to select study participants in collaboration with the University Clinic for Internal Medicine I and the Paracelsus 10,000 Study.

According to the NCEP ATP III definition, metabolic syndrome is present if three or more of the following five criteria are met: (NCEP, 2001):

- waist circumference > 102 cm (men) or > 88 cm (women)
- fasting triglyceride (TG) level over 150 mg/dl or Rx

- fasting high-density lipoprotein (HDL) cholesterol level less than 50 mg/dl (women) or 40 mg/dl (men) or Rx
- blood pressure over 130/85 mmHg or Rx
- fasting blood sugar ove110 mg/dl or Rx

see also (Huang, 2009).

2.1.2 Prevalence and Public Health

The prevalence of MetS in the global general population ranges from 12.5% to 31.4%, and in Europe, it ranges from 22.3% to 31.5%, depending on the definition used. Additionally, the prevalence of MetS increases with a country's level of income (Noubiap et al., 2022).

Prevalence in Europe (EUR, WHO region), general population:

- AHA/NHLBI: 27,9 %
- ATPIII: 25,3 %
- IDF: 31,5 %
- JIS: 26,8&
- WHO: 22,3 %
- Germany: 25,7 % according to AOKN-Population 2019 (Schütte et al., 2023))

The high prevalence of this civilization disease calls for contextualized public health interventions to tackle these conditions (Noubiap et al., 2022).

2.2 Nature-based therapies & nature-based biopsychosocial resilience

Academic and policy interest in the potential benefits of exposure to nature for human health and well-being has grown exponentially (World Health Organization (WHO), 2020; J. Zhang et al., 2020). Research indicates that exposure to nature in various forms has positive effects on a range of health and well-being outcomes (c.f. a.o. Frumkin et al., 2017; Hartig et al., 2014; Twohig-Bennett & Jones, 2018).

Beneficial outcomes include reduced mortality (Rojas-Rueda et al., 2019) and a lower risk of developing chronic illnesses such as cardiovascular diseases, diabetes and depression (van den Bosch & Meyer-Lindenberg, 2019). In addition, studies have shown that exposure to nature can improve short-term mood and concentration (Collado et al.,

2017). Notably, during the COVID-19 pandemic, individuals with access to nature coped better during periods of lockdown than those without (Pouso et al., 2021).

Contact with nature can act as "vaccine" (Hartig et al., 1991), "immunization" (Parsons et al., 1998) or "buffer" (Cartwright et al., 2018; Høj et al., 2021; Van Den Berg et al., 2010; Wells, 2021) against stress. It has been found to have a positive impact on stress levels and coping mechanisms in both acute and chronic situations (Korpilo et al., 2018; Roe et al., 2017; Takayama et al., 2019; Wells, 2021).

Nature contact can help individuals build and maintain resilience, which refers to the availability of adaptive resources through three types of resources (White et al., 2023): (1) biological resilience (e.g. improved immune functioning), (2) psychological resilience (e.g. better emotion regulation capacities), and (3) social resilience (e.g. improved social relations). These three types of adaptive resources are referred to as **biopsychosocial resilience** (Davydov et al., 2010; White et al., 2023).

From a public health perspective, it is important to develop low-threshold nature-based therapy interventions that are grounded in a strong theoretical foundation and a robust body of evidence. The NATURE—MET-S study aims to make a contribution towards this goal.

2.3 Nature-based Therapies und MetS

The Austrian Moderate Altitude Studies (AMAS) were the first nature-based interventions to address metabolic syndrome. AMAS I (2000) focused on the indicators of metabolic syndrome, which include overweight, disturbed blood sugar and blood fat metabolism, as well as elevated blood pressure. These factors pose significant cardiovascular risks. AMAS II (2006) focused on individuals with high stress levels. The studies have demonstrated that an active connection with nature, which involves a combination of hiking and active or passive regeneration, at moderate altitudes in the Alps (between 1,500 and 2,500 meters) under the guidance of professional coaches, has positive effects on individuals with metabolic syndrome, as well as on clients suffering from stress. These effects include a reduction in blood pressure and heart rate, an increase in the circulation of endothelial stem cells, and a reduction in body weight without the need for specific dietary measures. Additionally, there are positive psychological effects such as improved sleep quality, wellbeing, and social and physical recuperation (Gunga et al., 2003; Neumayr et al., 2014; Schobersberger et al., 2003, 2005, 2010).

Therefore, it can be inferred that nature-based interventions are a safe and effective method for reducing symptoms of metabolic syndrome and improving human health and well-being. However, it should be noted that the studies mentioned above were

conducted in a holiday setting. The proposed study, NATURE-MET-S, will concentrate on integrating nature-based therapies into daily life. This is a novel but promising approach to the secondary prevention of metabolic syndrome.

NATURE-MET-S aims to provide reliable evidence for indication-specific nature-based therapies. In the context of the HORIZON EUROPE project RESONATE¹,, it also aims to provide guidelines for the development and implementation of regionally based, resilience-promoting nature-based therapies in health care.

2.4 Nature-based therapies, MetS and Health-related Quality of Life (Primary Outcome 1)

Metabolic syndrome has physiological consequences, including an increased risk of cardiovascular and cerebrovascular disease, diabetes II, chronic kidney disease, and increased mortality risk (Arenillas et al., 2007). Additionally, MetS is associated with reduced health-related quality of life (HRQOL) in the majority of studies (Saboya et al., 2016). The association exists in both directions: This association exists in both directions. An improvement in MetS is correlated with an improvement in HRQOL, as shown in a recent prospective cohort study (Y.-H. Lin et al., 2021).

Health-related quality of life (HRQOL) is a multidimensional construct that encompasses physiological, psychological, and social dimensions. It includes more than just statements about an individual's state of health (Ellert & Kurth, 2013). The concept is comprehensive and multidimensional, reflecting an individual's perception of their own health and well-being. It is suitable for evaluating the impact of nature-based therapies in general (Prossegger et al., 2019) and specifically on Metabolic Syndrome (Strauss-Blasche et al., 2006).

MetS, a complex and multi-faceted disease, can cause psychological, psychological, and psychosocial problems (Y.-H. Lin et al., 2021). Therefore, we will assess the possible change in HRQOL using a generic QOL measure - the SF-12 - to evaluate the quality of life of the MetS study population in the context of nature-based therapy in a controlled and longitudinal manner (Weinhardt & Richter, 2013).

2.5 Nature-based therapies, MetS and Allostatic Load (Primary Outcome 2)

Allostatic load is a widely used metric of health risk that can effectively measure the potential health impacts of nature-based therapy on individuals with metabolic syndrome.

¹ Resonate (resonate-horizon.eu)

Study protocol

This is based on the hypothesis that repeated exposure to environmental demands, such as stress, leads to a gradual dysregulation of multiple physiological systems. Stress hormones, a shift in sympathovagal balance, or the production of inflammatory cytokines are prominent indicators of response to environmental challenges. These primary allostatic mediators are followed by secondary mediators, which reflect biological alterations that accumulate over time and increase the risk of clinical disease. The factors that define the metabolic syndrome include HbA1C, HDL/LDL, triglycerides, BMI, and waist-to-hip ratio (McEwen et al., 2016; Osei et al., 2022).

According to allostatic theory, biological adaptations are centrally mediated in response to environmental factors. The Allostatic Load Index (ALI) is a simple aggregate of primary and secondary mediators (McCrory et al., 2023). This index is a valid tool and metric for the assessment of health risks: both in cross-sectional studies as well as in intervention studies (Adams-Campbell et al., 2021; Rosemberg et al., 2020; Suvarna et al., 2020).

Although diet and physical activity are commonly considered the two main factors in preventing and treating obesity and MetS, it is important to note that epidemiological research suggests that these factors do not fully explain the variance (Holmes et al., 2010). Therefore, it is necessary to explore other potential factors that may contribute to the development of these conditions. The use of the ALI as a primary outcome parameter in the present study and in the RESONATE project provides insights into other factors influencing MetS secondary prevention via the triadic interaction of 1) physical activity/green exercise - 2) biopsychosocial resilience/stress and 3) metabolic syndrome.

3 Rationale and Research questions

3.1 Research rationale

This study examines the effects of a multimodal nature-based therapy program for individuals with metabolic syndrome on their **biopsychosocial resilience**. The program consists of easy hikes on the Salzburg city mountains (Green Exercise) and naturebased mindfulness training².

As outlined by White et al. (2023) the concept of **biopsychosocial resilience** encompasses biological, psychological, and social elements:

² A detailed description of the intervention is provided in chapter 4.3 Intervention

Biological resilience pertains to biological mechanisms that facilitate an individual's capacity to respond to stressors and recuperate. Illustrative examples include diminished inflammatory responses or enhanced blood lipid levels.

Psychological resilience is defined as the capacity to cope with stressors at the psychological level. This encompasses the effective regulation of emotions, a conscious perception of oneself and one's environment, and a high level of self-efficacy.

Social resilience is the quality of interpersonal relationships, social support, and access to resources in the environment. Social resources, such as a strong social network and group activities, can promote social resilience.

The intervention to be tested is designed to enhance the biopsychosocial resilience of individuals with metabolic syndrome through a **combination of nature-based physical activity and mindfulness training**.

Exercise therapy represents an efficacious approach for the prevention and alleviation of the consequences of metabolic syndrome (Myers et al., 2019). Physical activity exerts regulatory effects on fat and glucose metabolism, enhances insulin action, lowers blood pressure, and improves blood pressure control (Golbidi et al., 2012). Moreover, it has been demonstrated that exercise improves sleep quality, which serves as an important protective factor in relation to MetS (Chaudhry et al., 2023; Koren et al., 2016). Additionally, a correlation has been established between exercise and a more positive mood and a higher quality of life (Mahindru et al., 2023). In comparison to indoor exercise, outdoor exercise, also known as "green exercise," has been demonstrated to elicit additional psychophysiological effects, including improved mood and higher emotional well-being (Niedermeier et al., 2017; Pasanen et al., 2014). These benefits may be particularly relevant for individuals with metabolic syndrome.

Mindfulness training has been demonstrated to be an effective intervention for improving a range of biopsychosocial conditions, including depression, anxiety, stress, insomnia, addiction, pain, and prosocial behavior (D. Zhang et al., 2021). With regard to metabolic syndrome, studies have indicated that mindfulness training can positively influence both causal parameters for the development of metabolic syndrome, such as chronic stress, and clinical key parameters of MetS.

Clinical studies have demonstrated, among other findings, an enhanced capacity to cope with stress, including a reduction in depressive symptoms (Momeni et al., 2016; Rosenkranz et al., 2013; van der Zwan et al., 2015), a reduction in blood pressure (Hughes et al., 2013; Momeni et al., 2016), a reduction in inflammatory responses

(Rosenkranz et al., 2013) and a general improvement in the metabolic profile through a reduction in triglycerides, total cholesterol and glucose levels (Xue et al., 2018). A study by Creswell and colleagues (2012) also provides evidence that mindfulness training can reduce feelings of loneliness. This is of particular relevance in the context of metabolic syndrome, as loneliness is both a risk factor for the development of metabolic syndrome (Henriksen et al., 2019) and a concomitant factor of the disease (Whisman, 2010). Moreover, a longitudinal study demonstrated that mindfulness training has a positive socio-economic impact, for instance, in the form of a reduced utilization of disability pensions (Fjorback, 2012).

In light of the aforementioned background, it can be hypothesized that the implementation of a nature-based therapy program, comprising green exercise and mindfulness training, may enhance the biopsychosocial resilience of individuals diagnosed with metabolic syndrome, when compared to a control group.

3.2 Research questions

A two-arm randomized controlled clinical trial (NATURE-MET-S) is to be conducted based on the initial situation described above.

The primary objective of the clinical study is to analyze the impact of a multimodal nature-based therapy combining green exercise and mindfulness training on biopsychological resilience in a sedentary population with metabolic syndrome and low nature contact prior to the study.

Primary outcomes to measure biopsychosocial resilience are:

1) Quality of Life and 2) Allostatic Load,

The secondary objective is to provide data on environmental, social, and economical aspects of the intervention to contribute to innovation actions and to establish nature-based therapies as secondary prevention measure in health care.

In addition to the NATURE-MET-S study, similar studies on nature-based secondary prevention of MetS are being conducted simultaneously in Padua (Nature-Met-P) and Barcelona (NATURE-MET-B) to compare different types of nature exposure. The three studies are jointly developed and implemented. Although these are not multicenter studies, they are three comparable nature-based intervention studies for people with MetS (Barcelona, Salzburg) or at risk of MetS (Padua). This allows for a comparison of the effects of different types of natural environments: 1) coastal blue in Barcelona, 2) urban green in Padua, and 3) rural mountainous in Salzburg

The following research questions are to be investigated in the NATURE-MET-S study:

- 1) What is the effect of a nature-based intervention on biopsychosocial resilience in patients with Metabolic Syndrome compared to a control group (T1 day 1, T2 day 35, T3 day 70)?
 - a. Does health-related quality of life improve? Primary Outcome
 - b. Does the Allostatic Load Index improve? Primary Outcome
 - c. Are there changes in vital and lung function parameters and in the complete blood count? *Secondary Outcome*
 - d. Are there any changes in psychological and health economic parameters? *Secondary Outcome*
- 2) How sustainable are possible effects of the nature-based intervention compared to the control group? (T1 day 1 -T4 day 180)?
 - a. Are there sustainable changes in psychological and health economic parameters up to day 180 (online questionnaire)? *Secondary Outcome*
- 3) How is the nature-based intervention evaluated by the study participants? (T1 day 1 -T4 day 180)?
 - a. individual sessions Primary Outcome
 - i. What possible positive and negative emotions are induced by exposure to nature?
 - ii. How was the natural exposure carried out (alone/group, public transport)?
 - iii. iii) Where did the natural exposure take place?
 - b. the whole nature-based intervention Secondary Outcome
 - i. Quantitative and qualitative via interviews

The parameters listed under point 3.a are collected using MyCap mobile app³.

³ https://projectmycap.org/

3.3 Study design

Study type:	Two-armed randomized controlled clinical study	
Study arms:	2	
Study centers:	Paracelsus Medical University, Institute of Ecomedicine	
	Department of Internal Medicine I	
	with Gastroenterology - Hepatology, Nephrology, Metabolism and Diabetology University Hospital Salzburg	
Sponsor:	Investigator sponsored and initiated trial / Funding: Horizon Europe RESONATE, Project Nr. 101081420	
Control group:	Yes (Waiting-List Control Design)	
Randomization:	Yes	
Allocation ratio:	1:1	
Observation period:	180 days	
Analysis:	Intention-to-treat	

4 Methods: Study participants, Intervention and Outcome Parameters

4.1 Study setting

The study aims to recruit 140 individuals aged 40-65 years with metabolic syndrome from the outpatient clinics of Internal Medicine I (University Hospital Salzburg) and eligible patients from the Paracelsus 10,000 Study (Frey et al., 2021) over a 6-month period. The participants will be randomly assigned to either the intervention or control group. The intervention arm will be conducted in two consecutive rounds in September 2024 and March 2025. The control group participants will undergo examination simultaneously with the intervention group. They will subsequently have the chance to participate in the nature-based therapy program, which follows a waiting-list-control design. The nature-based intervention comprises green exercise/hiking and nature-based mindfulness training on the Salzburg city mountains (Lymeus et al., 2020; Pichler et al., 2022). The nature-based intervention should have accessible starting and ending points via public transportation.

4.2 Inclusion and exclusion criteria

4.2.1 Inclusion criteria

Participation is open to individuals who fulfill all of the following inclusion criteria:

- Individuals aged between 40 and 65 of any gender who meet the internationally recognized criteria for metabolic syndrome according to the NCEP ATP III criteria (NCEP, 2001):
- 2) Metabolic syndrome is defined by the NCEP ATP III as present if three or more of the following five criteria are met:(NCEP, 2001):
 - 1. waist circumference > 102 cm (men) or > 88 cm (women)
 - 2. fasting triglyceride (TG) level over 150 mg/dl or Rx
 - fasting high-density lipoprotein (HDL) cholesterol level less than 50 mg/dl (women) or 40 mg/dl (men) or Rx
 - 4. blood pressure over 130/85 mmHg or Rx
 - 5. fasting blood sugar ove110 mg/dl or Rx
- Sedentary lifestyle: Category 1 (low physical activity) of the International Physical Activity Questionnaire – Short Form (IPAQ-SF)) (International Physical Activity Questionnaire, 2005)

- 4) Low nature users:
 - 1) Category 1, 2 und 3 of the Monitor of Engagement with the Natural Environment Survey (MENE) question "nature use" (Natural England, 2020)
- 5) Smartphone users

4.2.2 Exclusion criteria:

- 1) Acute contraindications:
 - a. Malignant hypertension
- 2) Contraindications or differential diagnosis
 - a. Severe respiratory or lung disease (COPD according to GOLD Standard 3 and 4, severe asthma, emphysema)
 - b. Arteriosclerotic event (e.g. myocardial infarction) < 6 months ago
 - c. Uncontrolled metabolic diseases (e.g. uncontrolled diabetes mellitus)
 - d. insulin-dependent diabetes mellitus
 - e. Diagnosis or treatment of a malignant disease < 3 years in the past
 - f. Orthopedic illnesses that do not allow participation in hikes
- 3) Factors that prevent or hinder participation in the intervention program
 - a. Alcohol abuse
 - b. Pregnancy
 - c. insufficient knowledge of German language (written and spoken)
- 4) Factors that prevent self-management
 - a. Presence or indication of clinical depression (< 13 points WHO-5)
 - b. Serious other untreated psychiatric illnesses (e.g. schizophrenia)
- 5) Certain medication intake
 - a. Taking preparations for weight reduction
- 6) Participation in another interventional study
 - a. within the period of the clinical trial (t1-t4) and less than 4 weeks before the start of the trial (t1)
- 7) Participation in therapeutic weight loss programs
 - a. within the period of the clinical study (t1-t4) and less than 8 weeks before the start of the study (t1), e.g. Optifast®52 Program

4.3 Intervention

Nature-based therapy (NBT) consists of the components green exercise/hiking and nature-based mindfulness training.

The hikes are designed to accommodate individuals with varying levels of fitness. Each hike lasts between 1.5 and 2 hours. Participants will traverse distances between 3 and 6 kilometers and ascend to elevations of up to 300 meters on the Salzburg city mountains. A heart rate monitor (wristwatch) will be provided to each participant, which will be calibrated to their specific gender, age, height, and weight. This monitor will be used throughout the intervention. It is recommended that participants complete the hikes within the range of 60-70% of their maximum heart rate (Steele et al., 2021). Additionally, it is advised that training be conducted at a medium level of exertion on the Borg scale (12-16) (Borg, 1982; Löllgen, 2004). A guided group is limited to a maximum of 15 participants and is accompanied by a hiking guide and a mindfulness trainer.

Mindfulness training is based on concentrative movement therapy (Stolze & Badura-MacLean, 2002), a body psychotherapy method that combines physical movements and concentration to promote awareness and mindfulness of one's own body. The objectives of this form of mindfulness training are threefold: firstly, to enhance body awareness through targeted movement exercises; secondly, to reduce stress and promote general well-being; and thirdly, to cultivate mindfulness by training individuals to focus their attention on the present moment.

Intervention group (Nature group) :

Week 1 (day 0 - day 7): Onboarding

- a. 3 x 1,5-2h Green Exercise (guided hikes on the Salzburg city mountains,
 3-6 km each, 100-300 hm, max. 15 people per group)
- b. Within these hikes, participants will receive 20 minutes of nature-based mindfulness training under the guidance of a therapist in a pre-selected restorative and safe location. It is important to note that participants will learn mindfulness training during the process so that they can continue to practice it independently.
- c. It is required that all participants engage in the guided hikes during the initial week of the program.

Week 2 – Week 5 (day 8 – day 35): Integration

- a. 3 x 1,5-2h Green Exercise per week (guided or self-guided hikes (participants can choose) on the Salzburg city mountains, 3-6 km each, 100-300 hm)
- b. During these hikes, participants will engage in 20 minutes of mindfulness training in a natural and safe environment.
- c. In weeks 2-5, participants may elect to embark on the hikes independently or to participate in the guided hikes.

Week 6 – Week 10 (day 36 – day 70): Self-guided

- a. 3 x 1,5-2h self-guided Green Exercise peer week (Hikes close to home according to prepared tour recommendations 3-6 km, 100-300hm)
- b. During these hikes, participants will engage in 20 minutes of mindfulness training in a natural and safe environment.
- c. In weeks 6-10, no further guided hikes will be offered; participants will be encouraged to conduct the sessions independently. During this period, participants will receive notifications to conduct the therapy sessions via the MyCap app. They will also be requested to complete the app-based questionnaire three times a week during the therapy sessions.

In weeks 11-26, participants will no longer receive reminders to complete therapy sessions. Similarly, they will no longer receive active requests to complete the app-based questionnaire.

The tour recommendations are located throughout Salzburg city to prevent repetition and promote self-determination.

The tour offers recommendations for hikes of varying difficulty levels. Following the initial guided hike, participants are classified according to their fitness level. This is achieved by measuring their heart rate during the hike using a heart rate monitor and by assessing their perceived exertion using the Borg scale (Löllgen, 2004).

The therapy sessions are documented at the location of the mindfulness training sessions using the smartphone app *MyCap*. MyCap is a free, mobile, REDCap-based application for study participants that can be installed on iOS and Android devices to collect the results reported by participants for a specific study previously created in REDCap. The integration of MyCap into REDCap provides a comprehensive and secure data collection system, which is particularly well-suited to longitudinal studies that require frequent requests for information from participants (Harris et al., 2022). The questionnaire asks about the current mood (SPANE, PRS), the perceived exertion, whether the therapy session is being conducted in a group or individually, and whether the patient used public transportation to get to the session (see also 4.4 Outcome parameters).

The aim of the intervention is to integrate nature-based physical activity and mindfulness training into everyday life.

Control group:

The control group participants will undergo examination simultaneously with the intervention group.

For ethical reasons, the control group participants will also be offered the intervention after the study (outside the clinical trial).

The intervention will be standardized to enable comparison of results with other study sites, namely Barcelona (NATURE-MET-B) and Padua (NATURE-MET-P).

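### The 60-70% heart-rate range and the heart-rate part of the fitness classification make no allowance for heart-rate-lowering drugs, which the criteria do not exclude (minor, cheap safety improvement)

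*Protocol*

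**What the plan says.** **Intensity.** Section 4.3 of the protocol sets one heart-rate range for everyone: "It is recommended that participants complete the hikes within the range of 60-70% of their maximum heart rate". The watch is one "which will be calibrated to their specific gender, age, height, and weight"; medication is not among these inputs. On its use the text says: "This monitor will be used throughout the intervention". A second guide stands beside the range: "Additionally, it is advised that training be conducted at a medium level of exertion on the Borg scale (12-16"). The section does not say how maximum heart rate is obtained.

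**Classification.** After the first guided hike participants are sorted by fitness level, next to tour recommendations of differing difficulty: "This is achieved by measuring their heart rate during the hike using a heart rate monitor and by assessing their perceived exertion", the latter on the Borg scale. No rule is given for turning heart rate into a level or for combining it with Borg.

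**Who can enter.** In section 4.2.1 one of the five metabolic syndrome criteria is "blood pressure over 130/85 mmHg or Rx", so drug treatment satisfies it. In section 4.2.2 the only medication exclusion is for weight-reduction preparations, and arteriosclerotic events are excluded only within the last 6 months. Heart-rate-lowering drugs are not mentioned anywhere in the protocol.

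**Supervision.** Week 1 is guided and compulsory, and weeks 2-5 may be guided or self-guided. Then: "In weeks 6-10, no further guided hikes will be offered". For that period section 4.3 adds: "They will also be requested to complete the app-based questionnaire three times a week during the therapy sessions". The app items listed in section 4.4.1 include perceived exertion but not heart rate. Section 6.1 has a study physician assess everyone at T1 and names only the eligibility decision as its result.

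**The concern.** A drug that holds heart rate down gives a lower reading for the same effort. Against a range built on a maximum that ignores the drug, that reading suggests the participant should work harder. In a classification that takes a low hiking heart rate as a sign of fitness, it suggests a more demanding tour. Both errors point the same way, towards more effort than intended, in people whom section 4.2.1 requires to be sedentary.

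The stake is participant safety and the intended dose of exercise in a subgroup. No endpoint, test or sample size figure depends on it.

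**Working it through.** The plan gives no figure on this point to reproduce. The check has a text part and an illustration.

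**1. Can the group enter?** Treated blood pressure counts towards inclusion, older cardiac events are allowed, and no heart-rate-lowering drug is excluded. The treatment entry names no drug class, so the text shows only that such participants are not kept out. It does not show how many there will be.

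**2. Could the maximum have been measured on the drug?** Sections 4.4.1 and 4.4.2 list resting heart rate, heart rate variability, blood pressure and spirometry, but no exercise test. With the four watch inputs, this makes a predicted maximum plausible. It does not prove it.

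**3. Size of the range error, if the maximum is predicted.** Let *f* be the fraction by which the true maximum lies below the maximum used. *f* is an assumption; the protocol gives no value, and no age formula is needed.

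- Range as a share of the true maximum: 60/(1 − *f*) to 70/(1 − *f*).
- Displayed reading for someone truly at 70%: 70 × (1 − *f*).

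| *f* (assumed) | Nominal 60-70% equals, of true maximum | Reading when truly at 70% |
|---|---|---|
| 0% | 60-70% | 70% |
| 5% | 63.2-73.7% | 66.5% |
| 10% | 66.7-77.8% | 63.0% |
| 15% | 70.6-82.4% | 59.5% |
| 20% | 75.0-87.5% | 56.0% |

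The reading drops below the lower limit of 60 once *f* exceeds 1 − 60/70 = 14.3%. Beyond that point, a participant already at the intended upper limit appears to be under-exerting. If the maximum were measured on treatment, *f* = 0 and the range would be right.

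**4. Classification.** No algorithm is stated, so the size of an error cannot be computed. If a lower hiking heart rate counts towards a higher fitness level, the drug moves the participant up on that part. Borg is the other part and does not depend on heart rate.

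**5. How much room is there for over-exertion?** Using the limits in section 4.3 (3-6 km, up to 300 m ascent, 1.5-2 h, including a 20-minute mindfulness stop):

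- Gross pace: 3/2 = 1.5 km/h to 6/1.5 = 4.0 km/h.
- Pace net of the stop: 3/1.667 = 1.8 km/h to 6/1.167 = 5.1 km/h.
- Steepest net ascent rate: 300/1.167 = 257 m per hour.

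**6. Sessions without a guided option.** Week 1: 3. Weeks 2-5: 4 × 3 = 12. Weeks 6-10: 5 × 3 = 15. Total 30, so 15/30 = 50% of the prescribed sessions have no guide available while the watch is still in use.

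**The case against.** The strongest reply is that nothing in the protocol is misstated. The range refers to each person's own maximum, and section 4.3 does not say that the watch settings produce it. Read literally, a participant's own maximum already includes any drug effect, and the range error disappears. Reading a low heart rate as fitness likewise presumes a classification rule that the section does not give. Advice by drug class could sit in an intervention manual or with the study physician.

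The safeguards are real too. Both intensity guides are advice, section 3.1 calls the hikes easy, and distance and ascent are capped. Borg is advised throughout and enters the classification. Week 1 is guided, severe conditions are excluded, and the app asks about exertion in the unguided weeks.

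Much of this stands. The range error is conditional on a predicted maximum, the classification error is a possibility, and the safeguards keep the exposure small. The reply does not remove the gap. Borg is offered in addition to heart rate, and no rule says which governs when the two point apart. No stated step links the T1 assessment to the range or to the classification. Exercise intensity is also part of the intervention, so a statistical analysis plan would not supply the rule.

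A reader might infer more: that participants on these drugs will be over-exerted or harmed, or that the protocol prescribes an age-based maximum. The documents support neither. They give no prevalence, no drug effect and no formula, and nothing maps Borg 12-16 to heart rate, so it cannot be said that the two guides will disagree. Nor does the silence of section 6.1 show that the physician gives no advice.

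**Conclusion.** The point holds as a low-severity, cheap safety improvement. Section 4.3 applies a heart-rate range and a partly heart-rate-based classification to everyone, while section 4.2 lets in people for whom heart rate can mislead. The direction of any error is towards more effort than intended.

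The conclusion rests on three assumptions: some participants take drugs that lower exercise heart rate; the maximum is predicted without regard to them (for the range); and a low hiking heart rate is read as fitness (for the classification). The share affected and the size of the effect are unknown. The illustrative figures for *f* of 5-20% show direction and scale, not harm.

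**What to change.** At the T1 physician assessment, record heart-rate-lowering medication as yes or no, and tell the participant what it means for the watch. Add to section 4.3, in substance:

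*For participants taking heart-rate-lowering medication, the Borg rating takes precedence over heart rate, both for exertion during the hikes and for the fitness classification. A heart rate below the 60-70% range is not a reason to increase effort. The upper heart-rate limit remains as a backstop unless the study physician sets an individual range.*

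The cost is one field and a brief instruction at a visit that already takes place, plus this addition to the text. Treatment status is already needed to apply the inclusion criteria, and Borg is already taken on the first hike. Endpoints, sample size and analysis stay as they are.

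There are two limits. In this subgroup, intensity and classification would rest on a subjective rating. The retained upper limit is also no tighter than today's: at an assumed *f* of 10% it is 78% of the true maximum, and at 20% it is 88%. It is a backstop only; the protection comes from letting Borg govern and from removing the prompt to push up to the lower limit.
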